6.9.1. Quantitative

Descriptive quantitative information will be provided for implementation measures (percentages, rates, mean, median, variance, 95% confidence intervals). This will include reporting data on attrition rates and loss to follow-up.

Descriptive quantitative information will be provided for sleep assessment.

Analyses of symptomatology measurements will not be focused on statistical significance but will be quantitatively detailed (estimated 95% confidence intervals, variance) to assess the likely range of treatment effects. Our study is not designed nor powered to detect statistical differences in measures over time. Exploratory analysis of the relationship between symptomatology variables will be undertaken.

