3. ABSTRACT

Background: Covid-19 lockdown regulations impact negatively on sleep and mental health. These impacts disproportionately affect individuals with pre-existing mental health difficulties. Sleep disorders, particularly insomnia, are common in first episode psychosis (FEP) and are associated with increased symptomatology. Mood and worry mediate the relationship between sleep and psychosis symptomatology. Cognitive Behavioural Therapy is effective in treating insomnia (CBTi). Pilot research suggests that insomnia is a tractable clinical target in psychosis. Digital CBTi (dCBTi) reduces both insomnia and paranoia, offering a non-contact intervention during Covid-19 lockdown and its aftermath.

Aims: To inform the development of a logic model to support dCBTi (Sleepio) implementation in FEP services.

Methods: People experiencing a FEP and Insomnia will be eligible to access Sleepio. Usage data will be collated. Symptomatology measures will examine changes in service user psychosis, insomnia, and mood symptomatology, and Covid-19-related worry at baseline and post-intervention. Service users and keyworkers will be invited to participate in semi-structured interviews to elicit their views of Sleepio implementation. We will summarise implementation data and describe changes in psychosis, insomnia, mood, Covid-19-related worry, and the relationships between these. A framework analysis will be used to analyse themes arising from interviews.

Impact: We aim to develop a logic model to support future implementation of Sleepio in FEP services.

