6.6 Recruitment and Consent

6.6.1. Sample Size

6.6.1.1 Service Users

The Esteem population includes ~250 service users, with ~150 new users per year. Around 80% would be expected to experience clinically significant sleep difficulties (~200/250) and around 50% to experience Insomnia Disorder (~125/250; Reeve et al., 2018a). It is difficult to estimate the rate of eligible persons who will be willing to participate and will be retained in the study. A sample of ~8 for use of the Sleepio intervention has been considered feasible in terms of study resource. Sample size throughout (e.g. recruitment, withdrawal, participation in follow-up) will act as implementation data. As the study is not designed to identify change in symptomatology measures, power calculations have not been carried out. We aim to recruit ~5 service users to participate in optional interviews.

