6.6.4 Randomisation

Service user participants will not be randomized to treatment. All service user participants will be provided with access to Sleepio. Research will focus on developing a model for the implementation of this intervention.

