6.7 Data Collection

6.7.1 Implementation Data

We will gather data on eligibility, consent rates and the rate of service user participants beginning intervention. We will gather data on clinical sleep disorder assessment outcomes. Sleepio intervention will span week 0 to week 10. Usage data will be collated throughout these 10 weeks via the application. This data will comprise the rate of completion of the six sessions contained in the intervention and of sleep diaries. These metrics will allow us to ascertain intervention adherence, attrition and completion. We will further record rates of attendance to complete symptomatology measures. In analysis, these data will be represented by rates and summary statistics.

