6.7.2 Measures

Symptomatology measures will be completed with service user participants using NHS Attend Anywhere or at in-person appointments at baseline (week -1), and at week 11. Researchers completing these appointments are NHS GGC employees with pre-existing access to Attend Anywhere. We will complete symptomatology measures using Online Surveys (<https://www.onlinesurveys.ac.uk/>; formally **Bristol Online Surveys**). Online Surveys is UK based, Data Protection Act 2018-compliant and has ISO certification. If sessions are undertaken in person, these measures will be completed on paper. The study researchers are not aware of any issues in relation to the suitability, ease of use or acceptability of these measures in this service user group. The baseline appointment will also allow participants to set up the Sleepio application and complete its initial assessment.

Service user participants will be assessed with measures of:

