6.7.2.1 Insomnia

Service users will be screened for insomnia after completing consenting procedures, using the Sleep Condition Indicator – 2 Item (SCI-02; Luik et al, 2019). This is a reliable and validated shortened screening measure for insomnia, which correlates well to full

insomnia measures. Service users who's scores are not indicative of insomnia will be ineligible for study participation.

Insomnia symptoms will be assessed using the Insomnia Severity Index (Bastien, Vallieres, and Morin 2001) at baseline and week 11. This is a brief self-report questionnaire, designed to assess the severity of nighttime and daytime components of insomnia. It is widely used, demonstrates good reliability and validity, and is responsive to change through clinical treatment.

Additionally, participants will be regularly prompted within the Sleepio intervention to complete the full Sleep Condition Indicator (SCI, Espie et al., 2012). SCI is an 8-item scale which measures sleep problems against DSM-5 criteria for Insomnia Disorder. It has good validity and reliability and is sensitive to change (Espie et al., 2014). These scores will be available for analysis by researchers.

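### Section 6.9.1 presents the symptom confidence intervals as a range for treatment effects, but a single arm with no comparator can only describe change from all causes

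*Protocol*

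**What the plan says.** Section 6.9.1 gives the symptom analyses a purpose: they "will be quantitatively detailed (estimated 95% confidence intervals, variance) to assess the likely range of treatment effects". The next sentence adds a caveat: "Our study is not designed nor powered to detect statistical differences in measures over time". Section 6.6.1.1 says something similar: "As the study is not designed to identify change in symptomatology measures, power calculations have not been carried out".

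The design is set out elsewhere. Section 6.6.4 states that "Service user participants will not be randomized to treatment" and that all of them get Sleepio. The synopsis enters the comparator as not applicable. Section 6.7.2 has the symptom battery taken remotely or at "in-person appointments at baseline (week -1), and at week 11". Two data streams are collected more often. Section 6.7.1 says "Usage data will be collated throughout these 10 weeks via the application", which includes sleep diaries, and Section 6.7.2.1 says "participants will be regularly prompted within the Sleepio intervention to complete the full Sleep Condition Indicator". Both come only from people using Sleepio.

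The Abstract describes the same analysis without any claim about treatment: "We will summarise implementation data and describe changes in psychosis, insomnia, mood, Covid-19-related worry, and the relationships between these".

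**The concern.** A treatment effect is a contrast between what happened with the intervention and what would have happened without it. The plan has data on the first only. Calling the interval a range for treatment effects attributes the whole pre-post change to Sleepio.

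The protocol itself gives reasons why symptoms might move anyway. Usual care is allowed to change during the study and may include sleep psychoeducation (Section 6.5.1). Section 4.1 expects restrictions to be altered in phases, and Section 4.6 links Covid-19 worry and the regulations to sleep, mood and psychosis symptoms, which are the outcomes measured here. Entry requires a low SCI-02 score (Section 6.4.1.1), so some regression to the mean is possible.

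What is at stake is the label. The logic model is to be built from the quantitative and qualitative data (Section 6.9.3), is to show outcomes of Sleepio (Section 5.5), and is meant to inform later routine care in the service (Section 11). A range reported as Sleepio's effect could carry through to it.

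**Working it through.** The protocol states no effect size, standard deviation or power for the symptom measures, so there is no planned figure to reproduce. The check has three parts.

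**1. What the interval estimates.** Write participant *i*'s change from week -1 to week 11 as

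*d*ᵢ = *s*ᵢ + *c* + *u*ᵢ + *e*ᵢ

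where *s*ᵢ is the effect of Sleepio, *c* a shift shared by all participants (for example, a change in restrictions), *u*ᵢ individual change from other causes (usual care, natural course, regression to the mean) and *e*ᵢ measurement error. The usual interval is

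mean(*d*) ± *t*(0.975, *n*−1) × SD(*d*)/√*n*.

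Its centre estimates the average of *s* + *c* + *u*. Adding a constant *c* to every *d*ᵢ leaves SD(*d*) unchanged, so the interval moves by *c* without widening. Isolating *s* would need a control group, an external benchmark or a repeated pre-treatment baseline, and the protocol has none. The repeated in-app scores and diaries do not help, because they also lack a comparator.

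**2. Precision is a separate matter.** In units of the SD of the change score, the half-width is *t*(0.975, *n*−1)/√*n*:

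| Participants with both measurements | Half-width |
|---|---|
| 8 (the planned number, approximately) | 0.84 SD |
| 6 (assumed) | 1.05 SD |
| 5 (assumed) | 1.24 SD |

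A larger sample would narrow these intervals but would centre them on the same all-cause change.

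**3. Whether a shared Covid-19 shift would average out.** Section 12 puts data collection in March to June 2021, giving months only. The day limits below are assumptions.

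- Widest reading, 1 March to 30 June: 121 days, and 121/7 = 17.3 weeks.
- Battery window, week -1 to week 11: 12 weeks.
- Largest spread of baselines: 17.3 − 12 = 5.3 weeks.
- Smallest overlap of any two windows: 12 − 5.3 = 6.7 weeks.
- Starting instead at the protocol version date, 12 March 2021: 110 days = 15.7 weeks, spread 15.7 − 12 = 3.7 weeks, overlap at least 12 − 3.7 = 8.3 weeks.

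A change in restrictions falling in the overlap of two windows reaches both participants and enters the mean change. Between-participant variation does not reflect it.

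**Illustration of another cause.** With no treatment effect at all, selection on a low screening score shifts the baseline-to-follow-up mean by about *r* × (1 − *k*) × φ(*z*ₚ)/*p*, in baseline SDs. Here *p* is the fraction selected, *r* the screen-baseline correlation and *k* the proportion of that correlation retained at follow-up. With *p* = 0.5, φ(0)/0.5 = 0.798. For *r* = 0.6 and *k* = 0.9 the shift is 0.6 × 0.1 × 0.798 = 0.05. For *r* = 0.8 and *k* = 0.6 it is 0.8 × 0.4 × 0.798 = 0.26. All three inputs are assumptions, and the conclusion does not depend on them.

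**The case against.** The strongest reply is that the protocol largely neutralises the phrase. The following sentence and Section 6.6.1.1 disclaim design as well as power, and a study that disclaims detecting change can hardly be claiming attributed change. The symptom objectives in Section 5.2 ask only for characteristics at two time points and how the measures relate, and the Abstract speaks of describing changes. Section 5.5 provides for other factors in the logic model, and Section 6.9.4 collates a timeline of restrictions as context. No test, decision rule or sample size depends on the phrase.

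Much of this stands, and it is why the point is minor. The report could mislabel the change, but the protocol as a whole does not make that certain. The reply does not remove the mismatch, however. The caveats concern detecting change, not attributing it. The timeline and the other factors give context but separate nothing numerically. The Abstract shows that the authors had the fitting description available, so Section 6.9.1 should agree with it.

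Two further criticisms are fair. The overlap figures are outer bounds that show a shared influence is possible. They do not show that any restriction changed inside the overlap or affected symptoms, since the protocol dates no such change. Also, the word in Section 5.5 marking the logic model's content as hypothesised may qualify only the context, so it offers limited reassurance about how outcomes would be presented.

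**Conclusion.** The concern holds, as a minor point. The stated purpose of the intervals goes beyond what the design can support: they describe within-participant change from all causes between week -1 and week 11. This follows from the design and needs no assumption about numbers.

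The size of the non-Sleepio component cannot be calculated from the protocol. The overlap of at least about 6.7 weeks (8.3 if collection starts at the version date) rests on assumed calendar limits for the months in Section 12. It shows only that a Covid-19 influence could be common to participants. The consequence is limited because the symptom results are secondary and descriptive.

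**What to change.** In Section 6.9.1, replace the closing clause that gives the purpose of the intervals with: *to describe within-participant change from baseline to week 11; these intervals are not estimates of a treatment effect*. This brings the section into line with the Abstract. Section 6.9.3 needs no change.

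The cost is one phrase of protocol wording. The planned intervals, data collection and sample are unaffected. The only thing given up is a claim that the design could not support.

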6.9.2. Qualitative

Information arising from qualitative interviews will be analysed using a framework analysis based on the MRC Complex Interventions framework.

6.9.3. Modelling

A logic model of Sleepio implementation in FEP services will be developed from quantitative and qualitative data.

6.9.4. Other

A timeline of changes to Scottish government regulations regarding Covid-19 will be collated in order to contextualize study data.

7. ETHICS, PROJECT AND DATA MANAGEMENT

7.1 Ethics

7.1.1 Ethics

The proposed project will be conducted in compliance with the principles of the Declaration of Helsinki (1996), the principles of GCP and in accordance with the UK policy framework for health and social care research.

7.1.2 Ethics Approval

Esteem service managers have confirmed Esteem service capacity and capability to undertake the project (see Service Manager Approval – V1). We will apply for NHS GGC Research and Development (R&D) approval. We will seek ethical approval from the NHS Research Ethics Committee (REC). This protocol and related documents will be submitted for review. The study will request approval from NHSGGC Information Governance.

FR will ensure that University of Glasgow Doctorate in Clinical Psychology Research Programme Lead 'Proceed to Ethics' letter, REC 'Favourable Opinion' and R&D approval are in place before recruiting.

7.1.3 Consent Processes

Participation will not commence without informed consent, including ensuring participant awareness of confidentiality and limits to confidentiality. Consent will be taken by researcher FR. All study participants will be provided with a written information sheet and a written consent form for the study. All participants will have been judged to be capable of providing informed consent. It will be emphasised that potential participants may wish to contact others before making up their mind and that there is no hurry to decide. It will be made clear that study participation status will have no impact on TAU care or their role in Esteem.

At an Attend Anywhere appointment, the researcher will talk the participant through the consent form, verbal consent will be sought and participants will be asked to initial and sign two copies of the consent form and return one. For service users this will be via pre-addressed envelope, for keyworker participants this will be via scanning and email or pre-paid envelope. One copy will be retained by the participant and the other by the research team. The copy retained by the research team will be scanned and stored electronically on University of Glasgow servers. The paper original will be destroyed.

Aspects of the consent process will be optional, for example for service users to participate in interviews pre- and post-intervention.

Potential service user participants will be made aware that the study may pose a risk of distress prior to consenting. Keyworkers will be informed of participating service users.

Participants will be made aware of who to contact should they experience distress and the limits of confidentiality if there is risk to the participant or other persons.

7.2 Project Management

AG will be responsible for monitoring all research procedures and will supervise researcher FR during the study. MS will act as field coordinator and supervisor during the study. FR and MS will be responsible for recruitment of service users and keyworkers. FR will be responsible for collection of measures, rates of consent, interviewing, data monitoring and management, analysis and report writing. MS will be responsible for staff training and supervision associated with the study and regarding sleep difficulties in FEP more generally (although contribution will be made by AG, LB and FR). Big Health Ltd (CE, AH and CM) will be responsible for providing Sleepio usage data. The research group (AG, MS, LB and FR) will meet bimonthly throughout the trial to monitor progress and achievements.

NHS GGC Research and Development and the NHS Scotland Research Ethics Committee will establish the ethical standard of the study protocol. AG will have the responsibility to fulfil all the research governance arrangements and liaise with the NHS.

7.3 Data Management

7.3.1 Data Collection

Implementation, measures and interview data will be collected by the project researcher FR, under the supervision of AG and MS. Big Health Ltd will collate usage data for Sleepio.

7.3.2 Data Management and Storage

Please see the Data Protection Impact Assessment (V3 – 03.03.2021) for this study. Personally identifiable data will be held separately from research data, which will be paired with anonymous participant IDs. Interview recordings will be saved against participant IDs, although these do contain non-anonymised data as they are video recordings. Transcriptions will have personal or identifiable information removed and will be saved against participant IDs.

Personal identifiable data (e.g. names, email addresses and telephone numbers) will be kept separately from research data and will be stored within NHS GGC premises and electronic servers. Interview video or audio recordings will be stored on NHS GGC servers. There will be a key which links participant IDs to personal identifiable data and participant IDs to Sleepio access codes. These will be stored separately from all research data, in locked folders in NHS GGC. These will never be stored in the University of Glasgow and can be accessed only by the lead researcher ([name]) and chief

investigator ([name]). Pseudonymized study data will not be identifiable without access to these anonymization keys.

The study will hold and analyse pseudonymised data outwith NHS GGC (at the University of Glasgow) in locked storage and password protected electronic files. This data will be held in accordance with NHS GGC and University of Glasgow policies, the Data Protection Act and the Data Protection Act 2018. Core research team members are all contracted staff of the University of Glasgow and NHS Greater Glasgow and Clyde. All researchers are trained in and will be familiar with current laws, rules and protocol (governed by the NHS, university ethics guidelines and the Data Protection Act 2018) regarding consent, anonymity and data storage.

No data will be sent from NHS GGC nor the University of Glasgow to Big Health. Pseudonymised usage data will be sent from Big Health to the University of Glasgow. The pseudonymized data will be labelled with the individual Sleepio access codes which researchers initially share with participants to enable them to access Sleepio for free. The list of paired access codes, participant IDs and participant names will be stored within NHS GG&C only, not the University of Glasgow. The pseudonymized data will not be identifiable without access to the anonymization keys. All data in the Sleepio system is encrypted both "in transit" and "at rest". This means that the data is protected en-route from users' computer to the Sleepio servers, and also protected once it reaches the final destination of the Sleepio servers. The research team will be provided with pseudonymized data assessed by Sleepio such as adherence to treatment, sleep diary, engagement and measures collected with the application. This will be shared using an encrypted file. This data may be compared to other pseudonymized data, stored by participant ID but will never be paired with identifiable personal information.

Personal identifiable data is captured directly by Sleepio and stored by Big Health Ltd as standard for users of its application (for example name, email address, age, sex). Big Health treat these data as confidential in line with appropriate UK, EU and US regulations for protecting data. This data is not collected for the purposes of this research. This data will **not** be transferred to the University of Glasgow and only pseudonymized data will be sent. Big Health Ltd retain this personal identifiable data for 5 years, after which it is deleted. App users can also request deletion of this data at an earlier time.

Prior to providing consent to participating in the study, participants will be made fully aware of how their study data will be handled and who will have access to it. Only those in the core research team (AG, MS, LB, and FR) will have access to study research data.

Following study completion, anonymized research data, consent forms and interview transcriptions will be held for 10 years, as per University of Glasgow policy. It will be stored in secure electronic folders and accessible only to the Chief Investigator.

8. HEALTH AND SAFETY

8.1. Researcher Safety Issues

Use of Attend Anywhere or Microsoft Teams in home environments may reveal researchers' personal information. Researchers will ensure this is used in private spaces, will use blur background functions and will adhere to Esteem operational policy around its use.

Recruitment, follow-up and data collection may require significant practical and emotional labour. Supervision and time-management skills will be used to manage this. Researcher availability and monitoring of inboxes will be made clear to participants to maintain boundaries.

8.2. Participant Safety Issues

Participant sample may be associated with impulsive, irrational or unpredictable behaviour, and/or poor emotional control. Service users will be considered for their suitability by their keyworker. Participating service users will be in active contact with services at the time of their participation. Prior to consenting, participants will be made aware that keyworkers will be informed of their participation and will be able to monitor their Sleepio usage and sleep diaries. Researchers have a duty of care to report significant risks to a participant or to others to the mental health team in the event of a disclosure. These limitations to confidentiality will be made clear during consent processes. Researchers will ensure that appointments are undertaken in private spaces.

Symptomatology measures and Sleepio intervention may be associated with emotional distress. Use of this application is novel to this participant group and may cause distress, particularly in those affected by paranoia regarding technological devices. Potential participants will be made aware of the risk of distress prior to consenting.

